8.2.4 Graphical Analyses

Bar chart (with means and error bars at each visit) of the following variables will be generated, separately, to explore their pattern of evolution over time (from baseline to Month 3) under the IKERVIS® treatment:

- CFS score
- FVA parameters (VMR and LogMAR FVA)
- OSI
- Variance of OSI

9 SAFETY ANALYSES

The safety-related measures collected in this study include systemic and ocular AEs, corrected and uncorrected distance visual acuity, slit-lamp biomicroscopy, dilated fundus examinations, and IOP. The Safety population will be used for all safety summaries.

All the safety-related measures will be summarized descriptively. Except systemic AEs, which will be summarized at the subject level, all the other safety-related measures, including ocular AEs, will be summarized for the analysis eyes and fellow eyes separately.

9.1 **Pre-treatment Events (PTEs) and Adverse Events (AEs)**

PTEs and AEs are defined in Section 4.4.1. PTEs and treatment-emergent AEs (TEAEs) will be summarized separately.

In the overall AE summaries, subjects with any AE(s) will be tabulated by the following types of AEs:

- AEs
- SAEs
- Related AEs
 - AEs related to the study medication
 - AEs related to artificial tears
 - AEs related to study procedures
- AEs leading to premature discontinuation
- Sight threatening AEs
- Case of special interest
- Death

The above summaries will be repeated for ocular AEs in the analysis eye, ocular AEs in the fellow eye, and non-ocular AEs, respectively.

Besides the overall AE summaries listed above, AEs will be tabulated by SOC and PT. A subject who experienced multiple AEs within a SOC or PT will be counted only once for that SOC or PT, respectively. SAEs, related AEs, and serious related AEs will be tabulated similarly. Ocular and systematic AEs will also be summarized separately.

In addition, AEs will be tabulated by the following categories:

- SOC, PT, and maximal severity
- SOC, PT, and relationship (related to study medication, study procedure, or artificial tears)
- SOC, PT, maximal severity, and relationship (related to study medication, study procedure, or artificial tears)

Ocular AEs will be summarized for the analysis eye and fellow eye separately. Any ocular AE that occurred simultaneously to both eyes will be counted once for both the analysis eye and the fellow eye. Sight-threatening AEs and cases of special interest will be summarized by type of events specified in Section 4.4.1.2 and Section 4.4.1.3.

AEs, AEs leading to discontinuation, SAEs, sight-threatening AEs, case of special interest, and death, if any, will be listed separately.

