## 9.1.9 Documentation of Screen Failure

Investigators must account for all patients who sign informed consent. If the patient is found to be not eligible at Screening or Baseline visit, the investigator should complete the eCRF.

The primary reason for screen failure is recorded in the eCRF using the following categories:

- Pre-treatment event/AE.
- Did not meet inclusion criteria or did meet exclusion criteria.
- Major protocol deviation.
- Lost to follow-up.
- Voluntary withdrawal, specify reason.
- Study termination.
- Other, specify reason.

Patient numbers assigned to patients who fail screening should not be reused.

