## 10.1.6 SAEs

An SAE is defined as any untoward medical occurrence that at any dose:

- 1. Results in DEATH.
- 2. Is LIFE THREATENING.
  - The term "life threatening" refers to an event in which the patient was at risk of death at the time of the event; it does not refer to an event that hypothetically might have caused death if it were more severe.
- 3. Requires inpatient HOSPITALIZATION or prolongation of existing hospitalization.
- 4. Results in persistent or significant DISABILITY/INCAPACITY.
- 5. Leads to a CONGENITAL ANOMALY/BIRTH DEFECT.
- 6. Is an IMPORTANT MEDICAL EVENT that satisfies any of the following:
  - May require intervention to prevent items 1 through 5 above.
  - May expose the patient to danger, even though the event is not immediately life threatening or fatal or does not result in hospitalization.

PTEs that fulfil 1 or more of the serious criteria above are also to be considered SAEs and should be reported and followed up in the same manner (see Sections 10.2.1).

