#### 10.2 Procedures

## **10.2.1** Collection and Reporting of AEs

#### 10.2.1.1 PTE and AE Collection Period

Collection of PTEs will commence from the time the patient signs the informed consent to participate in the study and continue until the patient is first administered study medication or until screen failure. For patients who discontinue prior to study medication administration, PTEs are collected until the patient discontinues study participation.

Collection of AEs will commence from the time that the patient is first administered study medication. Routine collection of AEs will continue until the Final Visit.

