5.2 Safety Population

The *Safety* population will include all enrolled subjects who received at least one dose of the study medication and for whom any follow-up information is available. It will be the analysis population for safety analyses.

5.3 **Per-Protocol Population**

The *Per-Protocol* (PP) population will be a subset of the FAS subjects. It includes all FAS subjects without any of the following protocol deviations that could affect the primary efficacy endpoint.

- Failing to fulfill certain inclusion/exclusion criterion(a)
- Has a significant protocol deviation that could alter his/her efficacy outcome to treatment
- Without the primary efficacy measures of CFS, VMR, and OSI at the Month 3 visit
- Other significant protocol deviations identified by Santen's study team

Santen's study team will review all protocol deviations and identify subjects to be excluded from the PP population before the database lock.

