6 GENERAL CONSIDERATIONS

Statistical analyses will be performed based on this SAP by the Biometry Unit of Euraxi, a contract research organization (CRO) based in Joué Les Tours, France.

Unless specified otherwise, all efficacy analyses will be performed using data from the analysis eye of FAS subjects, and all safety variables will be analyzed separately for both the analysis eyes and the fellow eyes on the Safety population.

Continuous variables will be summarized using descriptive statistics such as number of observations (n), mean, standard deviation, median, minimum, and maximum. Categorical variables will be tabulated using frequency (n) and percent (%).

All statistical testing will be conducted at a significance level of 0.05 (two-sided) unless specified otherwise. No statistical testing will be conducted for safety measures.

All data manipulations, descriptive summaries, and statistical testing will be performed using SAS Version 9.4 or later.

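### The pre-treatment event (PTE) tables in SAP 9.1 are run on dosed patients only, so every PTE in a patient who was never dosed is left out of them

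*SAP*

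**What the plan says.** SAP 9 sets one population for its tables: "The Safety population will be used for all safety summaries". SAP 6 gives the same rule in general form: "all safety variables will be analyzed separately for both the analysis eyes and the fellow eyes on the Safety population". SAP 5.2 defines that population as "all enrolled subjects who received at least one dose of the study medication and for whom any follow-up information is available".

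SAP 9.1 covers both PTEs and adverse events and promises that "PTEs and treatment-emergent AEs (TEAEs) will be summarized separately". It names no other population for the PTE part. SAP 5 defines only the Full Analysis Set, Safety and Per-Protocol populations, and all three require dosing. SAP 10, which records departures from the protocol, is silent on the point.

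The protocol collects more than these tables can show. Under section 10.2.1.1, PTE collection starts at consent and is to "continue until the patient is first administered study medication or until screen failure", and patients who discontinue before dosing are expressly covered. Section 9.1.9 lists "Pre-treatment event/AE" first among the reasons for screen failure. Section 10.1.6 adds that "PTEs that fulfil 1 or more of the serious criteria above are also to be considered SAEs".

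**The concern.** A PTE occurs before the first dose by definition, so a table of PTEs should cover the people at risk of one. Here the table admits only those who went on to be dosed. A patient whose event during the wash-out stopped them from starting treatment is exactly the patient the table cannot contain.

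The pre-dose phase carries exposures that the study itself imposes. Patients stop their previous dry eye therapy (Protocol 6.1 and 9.1.4) and use sponsor-supplied tears. They have fluorescein instilled at Screening, and the Schirmer test and tonometry are done at Baseline before the first dose. Protocol 4.3 names allergy to fluorescein, anaesthetic drops or artificial tears, and irritation from the Schirmer test, among the risks of taking part. SAP 9.1 tabulates events by relationship to artificial tears and to study procedures, and both exposures begin before dosing. If serious PTEs occur in undosed patients, they count as SAEs under the protocol and yet fall outside the planned tables.

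**Working it through.** The plan gives no figure to reproduce, so the check is on the definitions, followed by simple arithmetic on the direction of the error.

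**Who can be in the table**

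1. Let C be all who consent, W those who enter the wash-out, D those dosed, and S the Safety population. By SAP 5.2, S lies inside D.
2. Patients who fail the entry criteria at Baseline leave without study medication (Protocol 6.1, SAP 3.1), and those who fail at Screening never reach dosing. All screen failures therefore lie in C but outside D.
3. Screen failures and S do not overlap. The share of their PTEs that can enter the SAP 9.1 tables is 0%.
4. The loss covers every PTE in an undosed patient, whether or not it caused the failure. It also covers a PTE in a dosed patient with no follow-up information.

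**Direction for counts**

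The full count equals the tabulated count plus the patients with a PTE who are outside S. The second term is zero or positive, so the planned count is never too high.

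**Direction for percentages**

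Let a of D dosed patients have a PTE, and k of U undosed patients. Assume every dosed patient has follow-up. The planned table shows a/D; the full figure is (a + k)/(D + U). The planned figure is too low only if a/D < k/U, that is, only if undosed patients had PTEs more often than dosed ones.

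**Illustration**

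The protocol summary plans 33 enrolled to obtain 30 included. Assume that *included* means dosed and that all 3 others entered the wash-out and were not dosed: 3/33 = 9.1% of those enrolled fall outside the tables. SAP 3.3 reads the 30 as completers and Protocol 7.4.1 speaks of 33 included patients, so this split is an assumption. Assume also that a = 1. The planned table then shows 1/30 = 3.3% whatever k is.

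| PTEs among the 3 undosed (k) | Full figure | Planned table |
|---|---|---|
| 0 | 1/33 = 3.0% | 3.3% |
| 1 | 2/33 = 6.1% | 3.3% |
| 2 | 3/33 = 9.1% | 3.3% |
| 3 | 4/33 = 12.1% | 3.3% |

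At k = 0 the planned percentage is slightly too high; from k = 1 it is too low.

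**The actual trial**

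SAP 3.1 reports 17 enrolled. It does not say how many were dosed or how many failed screening, and in Protocol 6.1 enrolled patients still have the wash-out and the Baseline check ahead of them. The 17 cannot be taken as the number dosed, and the number of PTEs lost cannot be computed.

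**The case against.** The strongest reply is that little is lost in practice.

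- **Listings.** SAP 9.1 ends with listings of AEs, SAEs, sight-threatening events and deaths and names no population for them. SAP 4.4.1 treats a PTE as a kind of AE, and SAP 4.4.1.1 counts serious PTEs as SAEs. In a study this small, listings carry most of the detail. This stands in part: the events may be listed, but the SAP does not say that undosed patients are included, and a listing gives no rate.
- **Other routes.** SAP 7.1 tabulates disposition for all enrolled subjects, and serious PTEs follow the SAE reporting procedure in Protocol 10.2.2. Both are true. Disposition can show at most a reason category, without the event, its severity or its relationship, and expedited reporting is not an analysis.
- **Materiality.** PTEs cannot reflect toxicity of the study drug, and Protocol 12.6 asks for treatment-emergent tables only. Safety is descriptive with no testing. Fluorescein and sponsor tears continue after dosing, so related harm is also captured there. Recent topical ciclosporin and corticosteroid use in the eligible eye is already excluded (Protocol 7.2), so for many patients the wash-out mainly replaces their own tears with the sponsor's. This stands, and it keeps the point modest.
- **Denominator.** Patients who fail at the Screening Visit never enter the wash-out, so using all consented patients as the denominator would dilute wash-out risk. This stands and shapes the fix.
- **Ocular tables.** SAP 4.2.1 defines the analysis eye through inclusion criterion 4. A screen failure with no eye meeting that criterion has no analysis eye, so the tables by eye cannot be rerun unchanged. This also stands.

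A reader might infer two stronger things: that wash-out harm can only look smaller, and that these events are reported nowhere. The documents support neither. The first is true of counts but not of percentages, and the unrestricted listing sentence leaves the second open.

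**Conclusion.** The point holds for the summary tables. SAP 9 and SAP 6, read with SAP 5.2, exclude every PTE in an undosed patient from the PTE tables, although the protocol requires these events to be collected. This is a consequence of a stated rule, not a gap in detail.

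The conclusion rests only on the definitions. Its numerical effect is unknown: counts are understated or unchanged, percentages may err either way, and the number of affected patients could be zero. Treatment-emergent tables, on-treatment safety measures and the efficacy results are not touched. It should be corrected because the PTE tables cannot otherwise describe pre-dose harm, but it does not threaten the trial's main conclusions.

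**What to change.** In SAP 9 and 9.1:

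- Summarise and list PTEs on all consented patients, including serious, procedure-related and artificial-tear-related PTEs.
- Split the results into three groups: screen failure before wash-out, entered wash-out but not dosed, and dosed. Use all who entered the wash-out as the denominator for events during it.
- Present ocular PTEs at subject level, or by right and left eye, where no analysis eye is defined.
- State that the listings include undosed patients.
- Keep the Safety population for treatment-emergent events and on-treatment measures.

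No new data are needed. Protocol 11.1 requires an eCRF for every patient who consents, and Protocol 10.2.1.2 has all PTEs recorded on it. The cost is some SAP wording, one extra table population and an adapted layout for ocular events. The PTE figures may also look less favourable.

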9.2 Slit-lamp Biomicroscopy

For each biomicroscopy parameter rated on a 0-3 scale (0=None, 1=Mild, 2=Moderate, or 3=Severe) or 0-4 scale (0=None, 1=Mild, 2=Moderate, 3=Severe, and 4=Very severe), rating scores and shift from baseline will be summarized by analysis visit for the analysis eye and the fellow eye, separately. In addition, any worsening (increase) of ≥ 2 units from baseline will be listed.

For lashes, which are collected as Normal or Abnormal, rating scores and shift from baseline in status will be summarized by analysis visit for the analysis eye and the fellow eye, separately. Any worsening in status from Normal at baseline to Abnormal after baseline will be listed.

9.3 Uncorrected Distance Visual Acuity (UDVA)

UDVA will be collected on LogMAR scale and their values and change from baseline will be summarized, separately, using descriptive statistics such as number of observations (n), mean, standard deviation, median, minimum, and maximum by analysis visit for the analysis eye and the fellow eye, separately.

9.4 Best Corrected Distance Visual Acuity (BCDVA)

BCDVA will be collected on LogMAR scale and their values and change from baseline will be summarized, separately, using descriptive statistics such as number of observations (n), mean, standard deviation, median, minimum, and maximum by analysis visit for the analysis eye and the fellow eye, separately. Subjects with any BCDVA score of 2.0 or greater after baseline or BCDVA change from baseline ≥ 0.30 LogMAR will be listed.

9.5 Dilated Fundus Examination

Dilated fundus exam data will be collected as Normal or Abnormal. Rating scores and shift from baseline in status will be summarized by analysis visit for the analysis eye and the fellow eye, separately. Any worsening in status from Normal at baseline to Abnormal after baseline will be listed.

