# 7.2 Exclusion Criteria

Any patient who meets any of the following criteria will not qualify for entry into the study:

- 1. Any ocular abnormality that may interfere with aberrometry measurement (e.g. macular disease or any loss of transparency of intraocular structures such as cataract or vitreous haemorrhage ....), in the eligible eye.
- 2. Active herpes keratitis or history of ocular herpes.
- 3. History of ocular trauma in the eligible eye or history of ocular infection (viral, bacterial, fungal, protozoal) within 90 days before the Screening Visit in either eye.
- 4. Any ocular diseases other than DED requiring topical ocular treatment during the course of the study.

- 5. Patients with ocular rosacea and/or with severe blepharitis and/or Meibomian Gland Disease (MGD), in the eligible eye. Patients enrolled with mild to moderate blepharitis and/or MGD should be treated as appropriate during the study.
- 6. Patients with progressive pterygium.
- 7. Concurrent ocular allergy (including seasonal conjunctivitis) or chronic conjunctivitis other than dry eye.
- 8. Anticipated use of temporary punctal plugs in the eligible eye, during the study. Patients with punctal plugs placed prior to the Screening Visit are eligible for enrolment; however, punctual plugs must remain in place during the study.
- 9. Abnormal lid anatomy or blinking function in the eligible eye such as but not limited to entropion, ectropion.
- 10. Abnormalities of the nasolacrimal drainage system in the eligible eye.
- 11. Best corrected distance visual acuity (BCDVA) score  $\geq$  +1.0 LogMAR ( $\leq$  35 ETDRS letters,  $\leq$  20/200 Snellen or  $\leq$  0.1) in each eye.
- 12. Use of topical CsA (e.g. IKERVIS®, RESTASIS®), tacrolimus or sirolimus within 90 days before the Screening Visit in the eligible eye. These treatments are also prohibited in both eyes during the course of the study, except IKERVIS® which will be administered as study treatment.
- 13. Use of topical corticosteroids, antibiotics, pilocarpine, antihistamines, or BAK preserved Intraocular Pressure (IOP) lowering medications within the 30 days before Screening Visit, in the eligible eye.
- 14. Patients with diffractive multifocal intraocular lenses, in the eligible eye.
- 15. Any ocular laser/surgery in the eligible eye within 90 days of Screening Visit.
- 16. Patient refusing to discontinue the use of contact lenses in the eligible eye, during the study.

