## 9.3.5.4 Dilated Fundus Examination

A dilated fundus examination will be performed after use of mydriatic eye drops to dilate the pupil in order to evaluate for posterior segment diseases. Abnormal outcomes will be described.

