4.4.2.4 Dilated Fundus Examination

A dilated fundus examination will be performed after the pupil is dilated at the Baseline and Month 3/early termination visits in order to evaluate for posterior segment diseases. It will be rated as normal or abnormal.

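### The fundus and lash worsening rules cannot flag a new abnormality in an eye already abnormal at baseline; it is reported as unchanged

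*SAP*

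**What the plan says.** **Fundus.** SAP 4.4.2.4 says of the dilated fundus examination: "It will be rated as normal or abnormal". SAP 9.5 repeats that "Dilated fundus exam data will be collected as Normal or Abnormal", and then gives two outputs. The summary: "Rating scores and shift from baseline in status will be summarized by analysis visit for the analysis eye and the fellow eye, separately". The listing: "Any worsening in status from Normal at baseline to Abnormal after baseline will be listed".

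**Lashes.** SAP 9.2 uses the same two-level approach: "For lashes, which are collected as Normal or Abnormal, rating scores and shift from baseline in status will be summarized by analysis visit", with a listing restricted to a move from Normal to Abnormal.

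**Graded slit-lamp parameters.** SAP 9.2 summarises all grades and shifts by visit for each eye and, in addition, "any worsening (increase) of ≥ 2 units from baseline will be listed". That listing rule has no condition on the baseline grade.

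**Descriptions.** Protocol 9.3.5.4 says of the fundus examination: "Abnormal outcomes will be described". For lashes, the grading scale in Protocol Appendix A-VII and SAP Appendix A asks that an abnormal finding be specified. The SAP plans no use of either description.

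**Who may be abnormal at baseline.** Exclusion criterion 1 (Protocol 7.2) bars "Any ocular abnormality that may interfere with aberrometry measurement", but only in the eligible eye.

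**The concern.** A two-level status can show only the first step from normal to abnormal. Once an eye is Abnormal, anything further that happens to it leaves the status where it was. A fundus with an old abnormality at baseline and an additional, different one at Month 3 is therefore reported as unchanged, and the listing meant to bring out worsening does not contain it. The same holds for lashes.

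This matters because change in the dilated fundus examination at Month 3 is a named safety evaluation (Protocol 5.2.2.2, SAP 2.2.2.2), and overall ocular safety is a secondary objective (Protocol 5.1.2, SAP 2.1.2). For eyes abnormal at baseline, a report that fundus status did not worsen would follow from the coding and would not be an observation. Fellow eyes are part of this: Protocol 6.1 and 8.1.4 have the drop instilled in each eye, and SAP 9 summarises fellow eyes for safety.

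**Working it through.** The plan gives no figure on this point to reproduce. The check applies each rule to every possible move from baseline to a later visit.

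**Inputs**
- Fundus and lashes: two levels; listed only if Normal at baseline and Abnormal later (SAP 9.5, 9.2).
- Meibomian glands, conjunctival erythema, anterior chamber inflammation, lens, vitreous: grades 0 to 3 (SAP 4.4.2.1).
- Lid erythema, lid oedema, conjunctival oedema, tear film debris: grades 0 to 4 (SAP 4.4.2.1).
- Graded parameters: listed if the increase is at least 2 units (SAP 9.2).
- Enrolled: 17 patients (SAP 3.1).

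**Step 1: two-level rule**

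| Baseline | Later | Shift summary | Listed |
|---|---|---|---|
| Normal | Normal | unchanged | no |
| Normal | Abnormal | worsened | yes |
| Abnormal | Normal | improved | no |
| Abnormal | Abnormal, same finding | unchanged | no |
| Abnormal | Abnormal, new finding | unchanged | no |

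The last two rows fall in the same cell. From an abnormal baseline, 0 of the 2 possible transitions can be listed, and new disease cannot be told from stable disease in either output.

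**Step 2: graded rule**

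On a scale from 0 to k there are k(k+1)/2 upward moves. A rise of at least 2 from baseline grade b requires b + 2 ≤ k, that is b ≤ k − 2. Summing over b gives k(k−1)/2 listed moves; the k one-step moves are not listed.

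| Scale | Upward moves | Listed | Not listed |
|---|---|---|---|
| 0–3 | 3×4/2 = 6 | 3×2/2 = 3 (0→2, 0→3, 1→3) | 0→1, 1→2, 2→3 |
| 0–4 | 4×5/2 = 10 | 4×3/2 = 6 (0→2, 0→3, 0→4, 1→3, 1→4, 2→4) | 0→1, 1→2, 2→3, 3→4 |

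Restricted to an abnormal baseline (grade 1 or more):
- 0–3 scale: 3 upward moves, 1 listed (1→3).
- 0–4 scale: 6 upward moves, 3 listed (1→3, 1→4, 2→4).

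So the graded rule can fire from an abnormal baseline. It can never fire for an eye one grade below the top: baseline 2 on a 0–3 scale, baseline 3 on a 0–4 scale. Among rises to the top grade, only 2→3 and 3→4 are unlisted. Unlike the last row in Step 1, these moves have their own cell in the shift table; what is missing is the patient-level listing.

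**Step 3: can baselines be abnormal?**
- Fundus, eligible eye: limited by exclusion 1, which names macular disease.
- Fundus, fellow eye: exclusion 1 does not apply. Exclusion 24 is not tied to the eligible eye, but it operates only where a disorder could interfere with procedures or interpretation.
- Slit lamp: exclusion 5 expressly allows mild to moderate blepharitis or Meibomian gland disease, so raised Meibomian grades at baseline are foreseeable.

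The documents give no proportion of eyes abnormal at baseline, so the number of eyes exposed to the gap cannot be computed.

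**The case against.** The strongest reply is that the examination listings are not the main safety route. Protocol 10.1.5 requires a worsening or complication of an existing condition after the start of study medication to be recorded as an adverse event, with a term that captures the change. Protocol 10.1.3 makes sight-threatening events serious. SAP 9.1 tabulates ocular adverse events by eye and lists adverse events. SAP 9.4 lists a change in best corrected acuity of at least 0.30 LogMAR, and SAP 9.6 an intraocular pressure rise of at least 10 mmHg, whatever the fundus looked like at baseline. The study is exploratory and single-arm, tests a marketed product, and plans no safety testing.

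Most of this stands and limits the consequence. It does not close the gap. Adverse event capture rests on the investigator's report and, for degenerative conditions, Protocol 10.1.5 records worsening only when it exceeds what would be expected. The acuity listing catches only disease that has already cost vision at a study visit. Neither corrects a shift table that shows a new finding as unchanged.

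A second reply is that the remedy needs fundus descriptions, while SAP 9.5 says the data are collected in two levels and the case report form is not among the documents. That is fair, and the fix is conditional on it.

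Two stronger readings are tempting and not supported. A reader might infer that the slit-lamp rule also fails for every eye abnormal at baseline, or that no rise to the top grade is listed. Step 2 shows otherwise: 1→3 on the 0–3 scales, and 1→4 and 2→4 on the 0–4 scales, are all listed. A reader might also infer that new fundus disease in these eyes would go wholly unreported; the routes above show that it need not.

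**Conclusion.** The point holds for the fundus and the lashes. As written, the rules cannot flag an eye that is Abnormal at baseline, and a new, different abnormality is reported as no change. For the fundus this is mainly a fellow-eye problem.

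Its practical size is unknown. With 17 enrolled there are at most 2 × 17 = 34 eyes, and one affected patient would be 1/17, about 6%; nothing in the documents shows that any patient is affected. The conclusion assumes that SAP 9.5 and 9.2 are applied literally and that no unplanned use is made of the descriptions.

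The slit-lamp part is separate and minor: one-step rises to the top grade (2→3, 3→4) are missing from the listing but visible in the shift table. Where to set that listing threshold is largely a reporting choice.

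Overall this is an inexpensive improvement to safety reporting. It is not a flaw that undermines the study's safety conclusions.

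**What to change.** **SAP 9.5, and the lash rule in SAP 9.2.** In addition to Normal-to-Abnormal moves, list any post-baseline abnormality not described for that eye at baseline, showing both descriptions side by side. In the summary, split Abnormal-to-Abnormal eyes into those with a new finding and those without. State beforehand who makes the comparison and what counts as new (for example, a finding absent from the baseline description), and keep unclear cases as a category of their own.

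**If the descriptions are not in the database.** List all eyes Abnormal at both visits and say in the study report that status alone cannot separate stable from new disease.

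**Optional, SAP 9.2.** Extend the graded slit-lamp listing to an increase of at least 2 units or any increase to the top grade of the scale. This adds 2→3 on the 0–3 scales and 3→4 on the 0–4 scales. It also adds no other moves, since every larger rise to the top is already listed.

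**Cost.** A wording change, slightly longer listings, and a manual comparison of short free text for at most 34 eyes, needed only where an eye is Abnormal both at baseline and later. The comparison involves some judgement. No new examination or visit is required.
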